15.3 Dexamethasone for Oral Administration (DXM)

15.31 **Background:** Dexamethasone is an adrenal corticosteroid compound. Dexamethasone decreases inflammation by suppression of neutrophil migration, decreased production of inflammatory mediators, and reversal of increased capillary permeability; suppresses normal immune response. Dexamethasone's mechanism of antiemetic activity is unknown.

15.32 **Formulation:** Commercially available for oral administration as:
Tablets [scored]: 0.5 mg, 0.75 mg, 1 mg, 1.5 mg, 2 mg, 4 mg, and 6 mg
Solution, oral: 0.5 mg/5 mL (500 mL)
Solution, oral concentrate: Dexamethasone Intensol: 1 mg/mL (30 mL)

15.33 **Preparation, storage, and stability:** Refer to package insert for complete preparation and dispensing instructions. Store oral tablets at room temperature between 20°C to 25°C (60°F to 77°F). Protect from moisture. Dispense in a well-closed, light-resistant container as defined in the USP/NF. Store oral liquid at room temperature, do not freeze. Do not use if solution contains a precipitate. Refer to commercial package for drug expiration date.

15.34 **Administration:** Refer to the treatment section for specific administration instructions. May be taken with meals to decrease GI upset.

15.35 **Pharmacokinetic information:**
Onset of action: Prompt
Duration of metabolic effect: 72 hours
Metabolism: Hepatic
Half-life elimination: Normal renal function: 4 ± 0.9 hours; **Biological half-life:** 36-54 hours
Time to peak, serum: Oral: 1-2 hours
Excretion: Urine (~10%)

15.36 **Potential Drug Interactions:**
Cytochrome P450 Effect: Substrate of CYP3A4 (major), P-glycoprotein/ABCB1; **Induces** CYP2A6 (weak/moderate), 2C9 (weak/moderate), 3A4 (weak), UGT1A1
Increased Effect/Toxicity: Aprepitant, azole antifungals, calcium channel blockers, cyclosporine, estrogens, and macrolides may increase the serum levels of corticosteroids. Corticosteroids may increase the hypokalemic effects of amphotericin B or potassium-wasting diuretics (loop or thiazide); monitor. Refer to the package insert for a listing of other drugs.
Decreased Effect: Antacids and bile acid sequestrants may reduce the absorption of corticosteroids, separate administration by 2 hours. Aminoglutethimide, barbiturates, and CYP3A4 inducers may reduce the serum levels/effects of dexamethasone. Serum concentrations of isoniazid

may be decreased by corticosteroids. Corticosteroids may lead to a reduction in warfarin effect. Corticosteroids may suppress the response to vaccinations.

Ethanol/Nutrition/Herb Interactions:

Ethanol: Avoid ethanol (may enhance gastric mucosal irritation).

Food: Dexamethasone interferes with calcium absorption. Limit caffeine.

Herb/Nutraceutical: Avoid cat's claw, Echinacea (have immunostimulant properties)

15.37 **Known potential adverse events:** Consult the package insert for the most current and complete information.

Common known potential toxicities, frequency not defined:

Fluid and electrolyte disturbances, congestive heart failure in susceptible persons, hypertension, euphoria, personality changes, insomnia, exacerbation of infection, exacerbation or symptoms of diabetes, psychosis, muscle weakness, osteoporosis, vertebral compression fractures, pancreatitis, esophagitis, peptic ulcer, dermatologic disturbances, convulsions, vertigo and headache, endocrine abnormalities, ophthalmic changes, and metabolic changes. Some patients have experienced itching and other allergic, anaphylactic or hypersensitivity reactions. Withdrawal from prolonged therapy may result in symptoms including fever, myalgia and arthralgia.

15.38 **Drug procurement:** Commercial supplies. Pharmacies or clinics shall obtain supplies from normal commercial supply chain or wholesaler.

15.39 Nursing Implications:

15.391 Monitor regularly for hypertension, CHF and other evidence of fluid retention.

15.392 Advise patient of possible mood or behavioral changes, i.e., depression, euphoria, insomnia, even psychosis. Instruct patient to report any suspected changes to healthcare team.

15.393 Assess for symptoms of gastric ulcer, heartburn, or gastritis. Suggest antacids. Instruct patient to report symptoms to healthcare team if unable to control.

15.394 Evaluate signs of infection, particularly local candidal infections and treat appropriately.

15.395 Monitor blood glucose frequently.

15.396 Instruct patient to report frequent, unrelenting headaches or visual changes to healthcare team.

15.397 Advise patient that easy bruising is a side effect.

16.0 Statistical Considerations and Methodology

16.1 Overview:

This is a pilot study to determine the response rates (>PR) of the combination of an immunomodulator and dexamethasone in Multiple Myeloma (MM) patients of each clinically relevant biomarker. This combination will be evaluated in four cohorts: Cohort A (Smoldering MM), Cohort B (Newly Diagnosed MM), Cohort C (Relapsed/Refractory MM) and Cohort D (Relapsed on Len maintenance). This study will not utilize a formal statistical design but will focus more on estimation rather than hypothesis testing.

16.11 Primary Endpoint: The primary endpoint of this trial is to estimate (>PR) response rates (RR) after one cycle of treatment. Biomarkers of interest will be identified and categorized into clinically relevant groups (e.g. positive vs. negative) by evaluating baseline and post treatment (after cycle one) biospecimens. RR will be estimated within each biomarker.

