14.3 Metabolomics profiling

To determine if specific metabolite profiles within the bone marrow and peripheral blood plasma will be reflective of the metabolic phenotype within the clonal bone marrow plasma cells that predict for response to therapy with an IMiD.

Methodology: For this analysis, bone marrow and peripheral blood plasma will undergo large scale, untargeted metabolite profiling via liquid chromatography mass spectrometry. Differentially expressed metabolites in responder versus non-responders will be evaluated for the development of a potential biomarker predicting clinical response.

Sample type and timing: Bone marrow aspirate samples will be collected in (1) 5 ml EDTA (purple top) tube and placed on ice or a cool pack. Samples to be collected prior to cycle 1 and then prior to cycle 2.

Sample Destination:

[name]
Mayo Foundation
[name]
[name]

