16.2 Statistical Design

Due to the lack of data to identify relevant biomarkers, the estimation of RR would be of interest. In each group, the response rates will be examined to see if there's any preliminary evidence to suggest further studies. This study will not utilize a formal statistical design.

For each biomarker category, the RR will be estimated by the number of patients who achieve a PR or better divided by the total number of evaluable patients in each cohort. Exact binomial 95% confidence intervals for these rates will be calculated.

16.22 Sample Size: A maximum of 30 evaluable patients will be accrued in cohort A and B and 60 patients in cohort C and D respectively. We anticipate accruing an additional 2 in cohort A and B and 3 in cohort C and D to account for ineligibility, cancellation, major treatment violation, or other reasons. Therefore, the maximum projected accrual is 190 patients (A: 32, B: 32, C: 63 and D: 63).

16.23 Accrual Rate and Study Duration: The anticipated accrual rate is 6 evaluable patients per month. Therefore, the accrual period for this pilot study is expected to be approximately 32 months. The final analysis can begin approximately 35 months after the trial begins, i.e. as soon as the last patient has been observed for 1 months and allowing 2 months for data entry.

16.24 Other considerations: Adverse events, quality/duration of response, and patterns of treatment failure observed in this study, as well as scientific discoveries or changes in standard care will be taken into account in any decision to terminate the study

16.3 Analysis Plan.

The analysis for this study is planned to start after data maturity has occurred. It is anticipated that the earliest date in which the result will be available via manuscript, abstract or presentation after the last registered patient has been followed for at least 1 month.

16.31 Primary Outcome Analyses:

Each cohort (A-D) will be evaluated separately and independently.

16.311 Definition:

The primary endpoint of this study is RR after 1 cycle of treatment. RR is defined as a binary variable. A success will be defined as patient who achieve a response of a PR or better using the IMWG criteria (Section 11.0) after one cycle of treatment. All patients meeting eligibility criteria who have signed a consent form, who complete at least one cycle of treatment and have successfully submitted biospecimens (pre and post treatment) will be evaluable for the endpoint.

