16.32 Secondary Outcome Analyses

16.321 Biomarkers and RR will be analyzed using logistic regressions to identify predictive biomarkers.

16.322 RR among African American (AA) patients and white MM patients will be evaluated after one cycle of treatment. Chi-Square (or Fischer Exact) test and 95% confidence intervals will be estimated to compared AA and white patients descriptively.

16.323 Correlation between the depth of hematological responses and biomarkers will be estimated. Logistic regressions and chi square (or Fischer exact) testing will be utilized.

16.33 Data & Safety Monitoring:

The principal investigator(s) and the study statistician will review the study at least twice a year to identify accrual, adverse event, and any endpoint problems that might be developing. The Mayo Clinic Cancer Center (MCCC) Data Safety Monitoring Board (DSMB) is responsible for reviewing accrual and safety data for this trial at least twice a year, based on reports provided by the MCCC Statistical Office.

Adverse Event Stopping Rules: (Each cohort will be analyzed separately) The stopping rules specified below are based on the knowledge available at study development. We note that the Adverse Event Stopping Rule may be adjusted in the event of either (1) the study re-opening to accrual or (2) at any time during the conduct of the trial and in consideration of newly acquired information regarding the adverse event profile of the treatment(s) under investigation. The study team may choose to suspend accrual because of unexpected adverse event profiles that have not crossed the specified rule below.

Accrual will be temporarily suspended to this study if at any time we observe events considered at least possibly related to study treatment (i.e. an adverse

event with attribute specified as “possible”, “probable”, or “definite”) that satisfy either of the following:

- If 3 or more out of the first 10 treated patients experience grade 4+ non-hematological toxicities
- If after the first 10 patients have been treated, 30% of patients experience grade 4+ non-hematologic toxicities

We note that we will review grade 5 adverse events deemed “unrelated” or “unlikely to be related”, to verify their attribution and to monitor the emergence of a previously unrecognized treatment-related adverse event.

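### Exact 95% confidence intervals for response within biomarker groups will under-cover when the biomarker was chosen on response in the same 30 or 60 patients

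*Combined protocol and SAP*

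**What the plan says.** All references are to the combined protocol and SAP.

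- **No marker list.** Section 16.2: "Due to the lack of data to identify relevant biomarkers, the estimation of RR would be of interest".
- **Markers are found with the response data.** Section 14.3, on untargeted profiling: "Differentially expressed metabolites in responder versus non-responders will be evaluated for the development of a potential biomarker predicting clinical response". Section 16.321: "Biomarkers and RR will be analyzed using logistic regressions to identify predictive biomarkers". Section 14.4 adds intracellular metabolomics, genomics and transcriptomics as further sources of candidates.
- **Groups are then formed.** Section 16.11: "Biomarkers of interest will be identified and categorized into clinically relevant groups (e.g. positive vs. negative"), on the basis of the baseline and post-cycle-1 specimens. It gives no cut-off rule.
- **Response is estimated in those groups.** Section 16.11: "RR will be estimated within each biomarker". Section 16.2: "Exact binomial 95% confidence intervals for these rates will be calculated".
- **Size.** Section 16.2: "A maximum of 30 evaluable patients will be accrued in cohort A and B and 60 patients in cohort C and D respectively". Section 16.31 has each cohort analysed on its own.

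The documents contain no sample split, resampling, external validation set, multiplicity control or selection-adjusted interval. Section 16.1 calls the study a pilot with no formal design, aimed at estimation rather than testing.

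**The concern.** A Clopper-Pearson interval treats the responders in a group as a binomial count among patients whose membership does not depend on their outcome. If a marker is kept because its groups differed in response, that condition fails. The higher group has been picked partly because chance placed responders in it, and its interval is centred too high. The lower group errs the other way.

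Section 16.2 says the group response rates will be examined for preliminary evidence to justify further studies, and Section 1.2 hopes to identify patients who could be spared a third or fourth agent. A marker with no relation to response could show a large difference between groups and be taken forward with an interval that looks like valid support.

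**Working it through.** **Inputs from the plan.** Evaluable patients: 30, 30, 60 and 60. The plan's own total reproduces: 30+2 = 32 and 60+3 = 63, so 32+32+63+63 = 190, matching "the maximum projected accrual is 190 patients (A: 32, B: 32, C: 63 and D: 63"). The plan gives no precision or coverage figure beyond the nominal 95%.

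**Inputs assumed.** A true RR of 40% for every patient; M independent markers unrelated to response, with M = 1, 20 or 200 because the plan gives no number; and two cut-off rules, because the plan gives none.

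**Interval.** For x responders among n, the lower limit is the 0.025 quantile of Beta(x, n−x+1) and the upper limit is the 0.975 quantile of Beta(x+1, n−x). For 15 of 30 this gives 31% to 69%; for 30 of 60, 37% to 63%.

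**Simulation.**
1. Draw responses at 40% and M random marker orderings.
2. For each marker compute z = (p1−p2)/√[p(1−p)(1/n1+1/n2)]. Here p1 and p2 are the group response rates and p is the overall rate. Use either a median split fixed in advance or the best cut between the 20th and 80th percentiles.
3. Keep the marker with the largest |z|.
4. Compute the exact 95% interval in its higher-RR group and record whether it contains 40%.

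**Coverage of the nominal 95% interval, higher-RR group:**

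| Cohort size | Cut-off | 1 marker | Best of 20 | Best of 200 |
|---|---|---|---|---|
| 30 | Fixed median | 98% | 86% | 66% |
| 30 | Tuned to response | 90% | 60% | 29% |
| 60 | Fixed median | 96% | 76% | 51% |
| 60 | Tuned to response | 86% | 50% | 25% |

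Repeat runs agree to within about two percentage points.

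**Apparent effect from noise.** At n=30 the best of 20 null markers shows on average 59% v 21% with the fixed split and 71% v 16% with the tuned cut, when both true rates are 40%. As an example, 10 responders of 14 is 71% with an exact interval of 42% to 92%, which misses the true 40%.

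**Other true rates.** A separate run used true RRs of 30% and 50%, with tuned cuts limited to the 25th to 75th percentiles. Best-of-20 coverage at n=30 was 80.5% and 76.6% (fixed), and 62.4% and 60.4% (tuned). At n=60 it was 79.5% and 74.6% (fixed), and 55.2% and 52.1% (tuned).

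**Control.** In that run, one prespecified marker with a fixed median split kept 95.6% to 98.9% coverage in each group. Selection on response is therefore what causes the loss.

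**The case against.** **The cut-off need not come from response.** A reader might infer that the plan tunes cut-offs to response. It does not say so: Section 16.11 speaks of clinical relevance and of the specimens, and that could be response-blind. This stands, and it makes the tuned rows a worst case. It does not remove the problem, because Sections 14.3 and 16.321 select the marker on response, and the fixed-split rows show that selection alone costs coverage.

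**Some markers may be grouped in advance.** Section 12.3 records mSMART FISH risk in fixed categories, and Section 4.0 collects LDH and beta-2-microglobulin. The plan does not say whether these count as biomarkers of interest. If they are grouped by a prior threshold and reported whatever the result, their intervals are sound. It would overstate the case to say that every biomarker interval is invalid.

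**The intervals are not narrow.** A reader might expect falsely precise results. In these simulations the higher group's interval averages about 50 points wide at n=30 and 38 at n=60. The error is in where the interval sits.

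**It is a pilot.** The estimation-only label answers a complaint about type I error, and words such as preliminary and potential limit the consequence. But a study that reports estimates relies on its intervals, and the label does not restore their coverage.

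**The size is uncertain.** Correlated markers act like fewer markers, and truly predictive ones lose less. This also stands.

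**Conclusion.** Wrong as written, for one set of results: exact intervals for response within groups of markers that were selected on response. Following the plan gives intervals that are misplaced and cover less often than 95%. Under the stated assumptions, with 20 to 200 candidates, coverage is about 66% to 86% at n=30 and 51% to 76% at n=60 with response-blind cut-offs. If cut-offs are also tuned to response, it is about 29% to 60% and 25% to 50%. The direction follows from the plan's own sequence of steps. The size depends on the number of candidates, their correlation, the cut-off rule and the true RR, none of which the plan states. The overall RR and interval of each cohort, which answer the primary goal in Section 2.1, are not affected, so a reader should not infer that the primary estimate as a whole is invalid.

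**What to change.** In Sections 16.11, 16.2 and 14.3:

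1. Set marker cut-offs without the response data: an established assay or clinical threshold where one exists, otherwise a response-blind rule, such as a quantile, fixed before marker values are linked to response.
2. Report every marker screened, with false-discovery-rate control for the untargeted screen.
3. For any marker or cut-off chosen using response, report optimism-corrected group RRs from a bootstrap or cross-validation that repeats the whole selection in every resample. Label the plain exact interval as not adjusted for selection.
4. Reconcile the denominator. Section 16.2 and the Estimation paragraph under Section 16.31 divide by all evaluable patients in the cohort, which does not give a response rate within a biomarker category.

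The cost is SAP wording and real analysis work, with no new patients or samples. Response rates in marker-positive groups will look less striking, and the corrected estimates will be imprecise at n=30. Holding out patients for estimation would also restore coverage, but with wide intervals: 7 responders of 15 gives 21% to 73%. Resampling with clear labelling is therefore the more practical route.

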14.4 Multiple myeloma cell retrieval

Samples type and timing: For studies utilizing intracellular metabolomics as well as genomics and transcriptomics of the MM cells, 35 ml of bone marrow aspirate will be obtained in (6) 6 mL ACD (yellow top) tubes in addition to the 5

ml of bone marrow aspirate from the (1) 5 mL EDTA (purple top) tube prior to cycle 1 and then prior to cycle 2.

Sample Destination:

[name]
Mayo Foundation
[name]
[name]

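### Section 16 describes biomarkers only as groups, while the metabolomic and transcriptomic assays give quantitative levels; Sections 16.321 and 16.323 should say that such markers are analysed as continuous

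*Combined protocol and SAP*

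**What the plan says.** **Primary estimation.** Section 16.11 states: "Biomarkers of interest will be identified and categorized into clinically relevant groups (e.g. positive vs. negative". Section 16.2 then estimates a response rate per biomarker category, with exact binomial 95% intervals. Section 16.1 sets the aim: "This study will not utilize a formal statistical design but will focus more on estimation rather than hypothesis testing".

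**Secondary analyses.** Section 16.321 uses logistic regression to find predictive biomarkers and does not say whether a marker enters as a level or as a group. For depth of response, 16.323 says: "Logistic regressions and chi square (or Fischer exact) testing will be utilized".

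**Assays.** Under 14.3, "bone marrow and peripheral blood plasma will undergo large scale, untargeted metabolite profiling via liquid chromatography mass spectrometry", and "Differentially expressed metabolites in responder versus non-responders will be evaluated". Section 14.4 adds "intracellular metabolomics as well as genomics and transcriptomics of the MM cells".

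**Sizes.** Section 16.22 says: "A maximum of 30 evaluable patients will be accrued in cohort A and B and 60 patients in cohort C and D respectively". No cut-point, or rule for choosing one, is given for any marker.

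**The concern.** The only form of biomarker that Section 16 describes is a grouped one. LC-MS metabolite levels and transcript levels have no natural boundary between positive and negative, and 16.2 itself concedes that data to identify relevant markers are lacking. A cut-point therefore cannot be assumed to exist.

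Splitting a quantitative marker treats all patients on one side of the cut as alike. In cohorts of 30 or 60 that loss of information matters for Goals 1 and 3, which are to find predictive markers and to relate them to depth of response. An open cut-point also leaves room to choose it after response is known, which raises the false-positive rate.

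**Working it through.** **1. The plan's own figure.** Accrual: (30 + 2) + (30 + 2) + (60 + 3) + (60 + 3) = 190, as 16.22 states. The documents give no power, alpha, effect size or expected one-cycle response rate for any biomarker analysis, so there is no power figure to reproduce. Those inputs are assumed below.

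**2. Check by formula.** Assume equal numbers of responders and non-responders (m = n/2 each), a marker with SD 1 in both groups, and a mean difference d = 0.8.

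- Continuous: power = Φ(d√(m/2) − 1.96). For n = 60, Φ(0.8 × √15 − 1.96) = Φ(1.138) = 87%. For n = 30, Φ(0.8 × √7.5 − 1.96) = Φ(0.231) = 59%.
- Split at the midpoint: the proportions above the cut are Φ(0.4) = 0.655 and 0.345, a difference of 0.311. Power = Φ((0.311 − 1.96√(0.5/m)) / √(0.452/m)). For n = 60 this is 68%; for n = 30 it is 39%.
- Loss: 87 − 68 = 19 points and 59 − 39 = 20 points.

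**3. Simulation of the logistic analysis.** Model: logit P(response) = a + ln(OR) × X, with X standard normal and a set to give the stated response rate. Tests are two-sided at 5% for a single marker. The continuous marker is tested by likelihood ratio. The same marker, split at the sample median, is tested by likelihood ratio and by Fisher's exact test.

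| Response rate | OR per SD | n | Continuous | Split, logistic | Split, Fisher | Loss, logistic | Loss, Fisher |
|---|---|---|---|---|---|---|---|
| 40% | 2.5 | 60 | 88% | 69% | 58% | 19 | 30 |
| 40% | 2.5 | 30 | 62% | 39% | 24% | 23 | 38 |
| 40% | 2.0 | 60 | 70% | 52% | 40% | 18 | 30 |
| 30% | 2.5 | 60 | 85% | 66% | 53% | 19 | 32 |
| 30% | 2.5 | 30 | 58% | 39% | 23% | 19 | 35 |

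At a response rate of 40%, over OR 2 to 3 and n = 30 to 60, the loss is about 14 to 23 points with logistic regression and about 24 to 40 with Fisher. At OR 1.5 the logistic loss is about 8 to 11 points, because power is low either way. A repeat with 10,000 replicates per setting gave 13 to 23, 22 to 41 and 6 to 11 points. The ranges are therefore good to about 2 or 3 points.

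**4. What part is not information loss.** With no true effect, Fisher's test rejected in only about 1 to 3% of simulated cohorts at nominal 5%, so part of its loss is conservatism. The continuous likelihood-ratio test rejected in about 6% at n = 30, which slightly flatters it there.

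**5. Sensitivity.** Other runs covered response rates of 30, 50 and 70% and OR 1.5 to 4. With a median split, the loss was 3 to 22 points (score test against chi-square) or 9 to 41 (likelihood ratio against Fisher). Cuts at the 20th to 80th percentiles widened this to 2 to 66 and 8 to 80.

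**6. Multiplicity.** With 100 markers and a Bonferroni correction (both assumed), response rate 40% and OR 2.5, power is 37% continuous against 16% split at n = 60, and 10% against 4% at n = 30. Continuous coding still does better, but both powers are low.

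**The case against.** The strongest reply is that the categorising sentence belongs to the primary endpoint. A response rate within biomarker groups needs groups, and the stated aim there is estimation, so power is not the yardstick. That stands. A reader might infer that 16.11 itself costs power or is the wrong primary analysis; the documents do not support this.

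Second, 16.321 is compatible with continuous entry, and 14.3 compares metabolites between responders and non-responders without mentioning a cut. This also stands: the plan does not commit itself to splitting every marker in the search. But 16.11 is the only description of a marker in Section 16, and 16.323 names tests that need groups, so the laboratory and statistical sections remain unmatched.

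Third, Fisher's test appears in 16.323 for depth of response and in 16.322 for race, not in 16.321 for response rate. The Fisher figures above, computed for a binary response, therefore only illustrate what that test would cost.

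Fourth, n = 30 is not established for the secondary analyses. "Each cohort (A-D) will be evaluated separately and independently" stands under the primary outcome in 16.31, and Goal 1 names untreated smoldering MM and MM patients together. Pooling cohorts A and B would give 30 + 30 = 60.

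Finally, no assay is called the main one. Genomics is also planned, and a marker that is binary by nature, such as a mutation, loses nothing.

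**Conclusion.** The point holds as a conditional one. If quantitative markers are split for the analyses of Goals 1 and 3, the like-for-like logistic loss is about 14 to 23 points for odds ratios of 2 to 3 per SD. It is smaller for weak effects and can be larger with Fisher's test or an off-centre cut. Every input except the cohort size is assumed: one marker, two-sided 5%, response rate 40%, normal marker, median split. The loss is thus not a property of the protocol that can be read off its pages.

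A reader might go further and infer that grouping would miss most true markers. The figures do not support that in general: at n = 60 the split logistic analysis still detects 69% at OR 2.5 and 52% at OR 2.0. Power falls below one half at n = 30 with OR 2.5, or with Fisher at n = 60 and OR 2.0. Nor would continuous coding by itself make an untargeted search well powered, since multiplicity lowers both powers.

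The change is worth making because it recovers information from samples already planned, at almost no cost.

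**What to change.** In 16.321 and 16.323, state that quantitative markers enter the logistic (or, for depth of response, ordinal) models as continuous, for example log2-transformed and scaled per SD, with a simple check for non-linearity. Limit chi-square and Fisher tests to markers that are binary by nature or have a cut-point fixed before response data are seen. Keep the grouped response rates with exact intervals in 16.11 and 16.2 as the descriptive primary estimation.

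The cost is analysis-plan wording only: no extra patients, samples or assays. The minor downside is that odds ratios per SD are less immediate for clinicians; the grouped response rates remain for that purpose.
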